Performance Feedback Reports. Performance feedback reports are defined as “a summary of clinical performance of health care over a specified period of time aimed at providing information to health professionals to allow them to assess and adjust their performance.”⁵¹ As in our prior work,³⁰ a performance feedback report will be developed by the Dissemination Advisory Board using evidence-based approaches^{31,42} and then provided to facility Medical Directors for pretesting. We expect the report to emphasize the most relevant information about the new kidney allocation policy for dialysis facilities, including tailored, facility-specific information (from publicly available, national Dialysis Facility Report data that we have previously used in research analyses²⁹ and for facility-specific reports³⁰) on the mean time on dialysis for patients in that facility, since transplant eligible-patients with longer dialysis may be more likely receive a transplant faster, compared to those with shorter dialysis time. In addition, the report will emphasize transplant access performance measures, such as waitlisting and transplantation,

including the magnitude of racial disparity, detailing when a facility is performing below the national or regional average. Evidence-based strategies will be used for the communication piece.⁴⁵ For example, one figure may emphasize simple communication about the kidney allocation policy, whereas another report may emphasize benchmarking to compare how the facility compares to other facilities in that state or ESRD Network region. One figure may emphasize information about racial disparity in transplant access and show the proportion of AA patients within the facility with corresponding transplant access measures. Based on 108 comparisons from 70 studies in a Cochrane Review, feedback performance reports are most effective when they include an action plan.⁵¹ This report will offer consistent messaging regarding action plans (e.g., educating patients about transplant). Individualized reports will be emailed to facility staff as described below, but will also be made available for download on the same website as the educational videos and webinars.

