Educational Video for Staff & Patients –The Dissemination Advisory Board will develop a short educational video targeted to dialysis facility staff (nephrologists, nurses, & social workers) that describes the new kidney allocation policy and how it impacts dialysis facilities, as well as a video targeted to patients within facilities to explain in plain language (6th-8th grade level) the transplant process and allocation policy. These videos will be hosted on a website and usage tracked. We ([name], [name], [name], [name]) have prior experience making videos for patients and staff

Educational Webinar for Medical Directors and Facility Staff – [name] (a UNOS representative) has agreed to participate in the Advisory Board and on the educational webinar about the kidney allocation policy. Content will be approved by the Dissemination Advisory Board and targeted to Medical Directors and facility staff. We ([name], [name], [name]) have experience developing content and hosting webinars for dialysis facility staff (n=12 webinars in 2014 alone) with 81% attendance (<http://www.esrdnetwork6.org/improving-care/transplant.html>). The webinar materials will also be hosted on a website for study participants to access.

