Study Procedures – Because there may be significant heterogeneity in dialysis facilities and patient and staff populations across the 18 participating ESRD Networks, we will randomize dialysis facilities that were not included in formative testing within each ESRD Network region to either the multicomponent intervention (feedback report, webinar, and videos) or comparison group (usual care plus UNOS educational brochure). At baseline (Year 2, Q3-Q4), all eligible dialysis facility Medical Directors in both the intervention and control group will receive an email from their ESRD Network Executive Director a web-based survey (HIPAA-compliant surveymonkey) with informed consent. For those who consent to participate (in reporting secondary outcome measures), baseline surveys will then be administered. Within one week of this email (or immediately after for those that complete a baseline survey), all facility Medical Directors from participating facilities will be emailed a UNOS pamphlet and instructed to share with staff; intervention facilities will be emailed facility-specific performance feedback report and videos, and information about the educational webinar. At 3 months, all facility Medical Directors who consented to participate will be emailed follow-up surveys by their respective ESRD Network Executive Director to assess secondary outcomes. Our prior work has shown >90% response rates by Medical Directors when surveys are mailed directly from the ESRD Network.⁵³ Medical Directors will be offered an electronic gift card incentive (\$10) for participation.

Effectiveness Measure Outcomes – To test the effectiveness of this intervention, several outcomes will be assessed via surveys and surveillance data. Waitlisting data from 1 year post-intervention will be assessed using nationally available Dialysis Facility Report surveillance data in order to assess disparity reduction at the facility level. Follow-up surveys will be emailed to all Medical Directors at 3 months to test change in knowledge about the kidney allocation policy and whether Medical Directors have implemented

any staff training regarding the allocation policy within their dialysis facility, what methods the facility has used to educate ESRD patients about the kidney allocation policy, and whether the policy influenced facility Medical Directors' intent to refer more patients for transplantation.

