Measures are described below. Surveys will be pilot tested in formative phases and finalized with approval by the Dissemination Advisory Board.

1) Change in Waitlisting Disparity (Primary Outcome) – We will calculate facility racial disparity in waitlisting one year prior and post-intervention as the difference between the proportion of AA vs. whites waitlisted.

2) Change in Knowledge about the Kidney Allocation System (Secondary Outcome) – We will survey Medical Directors using a 20-question scale measuring knowledge about the kidney allocation system, and general transplant knowledge, based on a validated scale we have used among dialysis staff and patients.⁵⁴

3) Change in Staff Training about Kidney Transplant and the Allocation System (Secondary Outcome) – We will assess at baseline whether Medical Directors have trained their staff about transplantation and/or the details of the kidney allocation policy. We will ask whether the Medical Director provided training about transplant or the kidney allocation policy in the prior 3 months after intervention delivery, and information about training (e.g., did they hold a training session, send an email, watch video presentations, etc.). Details about trainings will be collected to inform best practices for staff training for future scale-up.

4) Evidence of Communication to Patients (Secondary Outcome) – To ensure that dialysis facility Medical Directors communicate information about the kidney allocation system to their staff and patients, we will track the educational video website usage by asking users to input user type, facility name, and location. This will allow us to track intervention dose and usage statistics such as number of uses by facility, time in application, etc. We have previously tracked other mobile educational initiatives through Google Analytics with success.⁵⁵

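### Video use is linked to a facility only through what the viewer enters, with no stated check; a facility-coded link would reduce attribution error cheaply

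*Combined protocol and SAP*

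**What the plan says.** Under Effectiveness Measure Outcomes, item 4 (Evidence of Communication to Patients), the protocol states "we will track the educational video website usage by asking users to input user type, facility name, and location". It then says what the entry is for: "This will allow us to track intervention dose and usage statistics such as number of uses by facility, time in application, etc". The same item adds "We have previously tracked other mobile educational initiatives through Google Analytics with success", which reports past experience and describes no facility identifier.

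Other sections bear on the same point:

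- **Educational Video for Staff & Patients:** "These videos will be hosted on a website and usage tracked". No login or access control is mentioned.
- **Study Procedures:** "intervention facilities will be emailed facility-specific performance feedback report and videos, and information about the educational webinar".
- **Performance Feedback Reports:** the individualized reports "will also be made available for download on the same website as the educational videos and webinars". How a facility is identified for that download is not stated.
- **Implementation effect measures:** the crude implementation index for a facility adds up the secondary outcomes, each split at its median. Table 2 lists four such outcomes, and communication to patients is one of them.

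**The concern.** The viewers include patients, and the planned minimum is 750 facilities across 18 Networks. If a viewer skips the facility field or enters a name that cannot be matched, the viewing is logged but belongs to no facility. If the viewer enters the wrong facility, it counts for another one. The documents describe no code, login, list of facilities to choose from, comparison with the randomized list, or rule for blank or unmatched entries.

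The completeness of entry may differ between facilities and between patients and staff. The number of uses by facility would then reflect how well the entry page was filled in as well as how much the videos were used. In a hybrid effectiveness-implementation study, a low recorded dose should mean low use. Here it could also mean poor data entry, and nothing planned would tell the two apart.

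**Working it through.** The documents give no video-use count, attribution rate or error rate, so there is no figure of the plan's to reproduce. The power statement concerns the waitlisting disparity and is not an input. The check has two parts.

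**1. Reading the sections together.** Item 4 names viewer entry as the link. The video section adds only that usage is tracked. The Google Analytics sentence is about earlier work. The report section shows that facility-specific material sits on the same site but not how it is accessed. Study Procedures shows that the sender knows the facility when the email goes out. So one linking method is stated, no check is stated, and facility identity is available at a point where the plan does not use it.

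**2. Illustration of size. All rates are assumed.**

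Model A (loss only):

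- True uses at a facility, U: Poisson with a gamma-distributed rate (shape 1), mean 4, 8 or 16.
- Facility attribution probability, p: beta with mean m and SD s. The beta parameters are mν and (1−m)ν, where ν = m(1−m)/s² − 1.
- Attributed uses, A: binomial(U, p).
- Outcome: the share of facilities for which U is above the median of U but A is not above the median of A, or the reverse.
- 200,000 simulated facilities.

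| m (s) | ν | Attributed count low by | Change side, mean 4 | mean 8 | mean 16 |
|---|---|---|---|---|---|
| 0.90 (0.10) | 0.09/0.01 − 1 = 8 | 10% | 8.8% | 3.7% | 3.7% |
| 0.70 (0.20) | 0.21/0.04 − 1 = 4.25 | 30% | 10.9% | 10.5% | 10.3% |
| 0.50 (0.25) | 0.25/0.0625 − 1 = 3 | 50% | 18.5% | 17.9% | 18.1% |

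The third column follows from E[A] = m × E[U]. With a mean of 8 uses and m = 0.90, for example, 0.90 × 8 = 7.2 are attributed. The 8.8% at mean 4 is largely a tie effect: the true median is 3 and the attributed median is 2. Counting facilities at or above the median, instead of strictly above it, widens the overall range to about 3.5% to 23%.

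Model B (loss plus wrong-facility credit):

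- 375 facilities, the planned minimum per arm, with mean uses 3, 10 or 30.
- 5% to 40% of entries lost, varying by facility, and 2% to 10% of the retained entries credited to a random other facility.
- With viewer entry alone, about 60% to 95% of uses are captured and 3.5% to 19% of facilities change side of the median.
- If an error-free coded link carries 80% of uses and 20% still rely on entry, capture is 1 − 0.2 × 0.40 = 0.92 to 1 − 0.2 × 0.05 = 0.99, and 0.6% to 4% of facilities change side.

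**The case against.** The protocol is short, and its silence does not prove that no other identifier was built. It says that users input the information, not that they type free text, so a list to choose from would fit the wording. Asking for location as well as name helps to resolve ambiguous names. These points stand: the claim is about what the plan states, and misspelling is only one possible route to error. A list would deal with spelling but not with skipped or wrong choices.

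Three stronger readings are tempting, and the documents do not support them.

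- **A reader might infer that total dose is understated by 10% to 50%.** It is not. A viewing with no usable facility entry is still a logged viewing on a tracked site, and a miscredited one is still counted. Only the facility-attributed count falls.
- **A reader might infer that the trial's main result is at risk.** The primary outcome comes from Dialysis Facility Report surveillance data and does not use these logs. The protocol emails the videos only to intervention facilities and ties no effectiveness claim to the index.
- **A reader might infer that a coded link removes the problem.** The email goes to Medical Directors, while the outcome concerns staff and patients. A viewer who reaches the site another way carries no code, and a forwarded link carries the sender's code.

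The logs are also not the only evidence on this outcome. The 3-month survey asks Medical Directors how patients were educated, and Other Measures lists receipt of the intervention and self-report.

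**Conclusion.** The point holds as a cheap improvement. The only stated link between a video use and a facility is the viewer's own entry, and no check is stated. The effect is confined to the facility-attributed use count and what is built on it: the communication-to-patients outcome, the facility-level dose and one of four index items.

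The documents do not allow the size to be determined. The 4% to 18% range for facilities changing side of the median rests entirely on assumed attribution of 50% to 90%, assumed variation between facilities and assumed use counts. It covers lost uses but not wrong-facility credit. Model B, which includes wrong credit on other assumed rates, gives a similar range. Both show only that errors of this kind could matter for a median-split item; neither estimates what happened in this trial.

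**What to change.** Amend item 4 of Effectiveness Measure Outcomes as follows:

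1. Put a unique facility-coded link in the email that already carries each intervention facility's report and videos. Supply the same code as a short code or QR for patient and staff devices.
2. Attribute use by the code.
3. Keep viewer entry for user type, as a fallback where the code is absent, and as a cross-check on forwarded links.
4. Report the share of uses attributed by code, by entered name and not attributed, and state how unattributed uses are handled in the facility counts.

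The cost is setting up one link per facility in emails that are already individualized, and getting the code onto the devices that patients and staff use. Some forwarded links will carry the sender's code, and the entered name will catch only part of these. Attribution error would fall but not disappear, and the reported shares would show how much remains.

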5) Change in Intent to Refer Patients to Kidney Transplantation (Secondary Outcome) – We will assess the current referral practices of facilities by surveying Medical Director about the estimated proportion of patients interested, eligible, and referred for transplant in their facility at baseline and at 3 months post- intervention. We will ask questions about the estimated % of patients referred for transplant by specific patient characteristics (e.g. age, race/ethnicity, SES, time on dialysis, etc). A similar survey has been used in our Network in the past⁵³ and will be finalized by the Dissemination Advisory Board in objective 1. Obtaining actual referral data is only possible for ESRD Network 6 dialysis facilities. However, our prior analyses examining dialysis staff-reported referrals and actual referrals to transplant centers show high correlation ($r=0.79$; $p<0.01$).

Implementation effect measures: We will use an adaptation of the RE-AIM (Reach, Effectiveness, Adoption, Implementation, and Maintenance) framework³⁸ for evaluating the public health impact of this health policy change.⁴⁵ This framework builds upon the conceptual models of Rogers⁵⁶ and Green and Krueger⁵⁷ in this hybrid effectiveness-implementation study. A description of each of these measures and how they are applied to evaluating the successful implementation of a policy intervention are described in the table above. Effectiveness and Adoption measures are described in detail above. Implementation will be assessed by calculating a composite measure, or 'crude implementation index' for each facility as the sum of each secondary outcome (dichotomized at the median). We will conduct qualitative analyses of select dialysis facility providers that were successful intervention implementers ($n=5$) and non-

Table 2. Re-AIM Components and Study Measures to Track Implementation

RE-AIM Components	Definition	Study Measures
Reach	Number or % affected by policy; population characteristics	1. % of participating facilities with racial disparities / all facilities with racial disparities 2. Comparison of participating vs. non-participating facilities
Effectiveness	Change in outcomes	Primary outcome: Racial disparity in waitlisting
Adoption	Proportion that adopt policy or intervention	Secondary Outcomes: 1. Knowledge about allocation system 2. Staff training about transplant & allocation 3. Communication to patients 4. Intent to refer for kidney transplantation

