Implementation	Extent to which an intervention is delivered as intended	1. Crude implementation index 2. Qualitative analysis of implementers vs. non-implementers
Maintenance	Long-term behavior change	Longer-term (1-year) adoption measures among a subset of facilities

implementers (n=5). At 1 year via phone interviews. These providers will be selected among the providers who completed the follow-up survey and already provided consent for the intervention. Phone interviews will be recorded and transcribed to help us better understand how to improve the intervention for the future. Providers who participate in the interview will be given \$30 gift cards as an incentive.

Other Measures. To explore potential moderators of the effectiveness of this system-level intervention, we will examine facility characteristics (region, facility size, profit status, etc), characteristics of patients in facilities (e.g., race, SES, comorbidities, etc), and neighborhood characteristics. We will include process measures for the intervention (receipt of intervention and self-report) to evaluate utility, value, satisfaction and reactions to intervention materials to ensure optimal future dissemination of interventions to other US dialysis facilities.

STATISTICAL ANALYSES

We will evaluate our main outcome of change in AA vs. white racial disparity reduction in waitlisting in the year post-intervention compared to the year prior to the intervention among the intervention vs. control facilities (intent to treat) using generalized linear models⁴⁸ to account for potential correlation of facilities within Networks. Secondary analyses will examine facility- and patient-level modifiers of the intervention. Change in each of the secondary outcomes will be examined. *We hypothesize that increasing provider knowledge about the allocation policy in facilities with racial disparities will reduce waitlisting disparities.* Follow-up interviews will be transcribed verbatim and a codebook will be developed for qualitative analysis. Thematic analysis of key facilitators and barriers will be conducted to inform practice change.⁵¹

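### The implementation index ranks facilities on the four Adoption outcomes and cannot show how far the intervention was delivered as intended

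*Combined protocol and SAP*

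**What the plan says.** In Table 2, Implementation is defined as "Extent to which an intervention is delivered as intended", with two measures: "1. Crude implementation index 2. Qualitative analysis of implementers vs. non-implementers". The paragraph on implementation effect measures defines the index for each facility "as the sum of each secondary outcome (dichotomized at the median".

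The Adoption row of the same table lists "1. Knowledge about allocation system 2. Staff training about transplant & allocation 3. Communication to patients 4. Intent to refer for kidney transplantation". These are secondary outcomes 2 to 5 in the numbered list of measures:

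- knowledge, on a 20-question scale;
- staff training, asked as whether training was given, with details of how;
- communication to patients, tracked through use of the video website;
- intent to refer, as the Medical Director's estimated proportions.

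Delivery information also appears in two other places. Under Other Measures the plan includes "process measures for the intervention (receipt of intervention and self-report", and gives their purpose as judging how useful and well received the materials were. Under the communication outcome, website users enter user type, facility and location, and the plan adds: "This will allow us to track intervention dose and usage statistics such as number of uses by facility, time in application, etc".

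The plan does not state which facilities supply the median (both arms or one), at which time point, how ties are handled, or what level of any item counts as delivered.

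**The concern.** The definition asks an absolute question: how much of the intervention reached facilities as planned? The measure answers a relative one: which facilities scored higher than the others on four outcomes? Because those four are the Adoption outcomes, two RE-AIM rows draw on the same data. A Medical Director who already knew the allocation policy and already intended to refer could pass two items without opening the report. Conversely, receipt of the feedback report, the central component of the intervention, contributes nothing to the score.

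At stake is the implementation half of Objective 2, which asks about the feasibility of implementing the report. The introduction defends the hybrid design partly because it has value even if disparities do not fall. If the primary result is null, the first question will be whether the intervention failed to arrive or arrived and did not work. The index named for this purpose does not address that question.

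**Working it through.** The documents give no figure for the index, so there is none to reproduce. The check is how a median split behaves for each kind of item. The distributions below are assumptions, because the documents give none. The parenthesis could be read as splitting the sum, but splitting each item is the more natural reading and is used here.

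**1. Overlap.** Index items: knowledge, staff training, communication, intent to refer. Adoption items: the same four. Training and communication lie close to delivery; knowledge and intent to refer are downstream responses. Receipt is in neither row.

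**2. Near-continuous item (intent to refer).** With sample median m, the share with X > m is 0.5. If every facility moves by c, the median moves to m + c and the share stays 0.5. Simulated shifts of 0, 1 and 3 SD each left 50% above. If all four items behaved this way, the mean index would be 4 × 0.5 = 2.0 at every level of delivery.

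**3. Knowledge score, 20 questions.** Taken as binomial(20, p):

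| p correct | median | share > median | share ≥ median |
|---|---|---|---|
| 0.50 | 10 | 41% | 59% |
| 0.70 | 14 | 42% | 61% |
| 0.85 | 17 | 40% | 65% |

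The share passing barely moves while the level rises from 50% to 85% correct.

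**4. Yes/no item (staff training, as it appears).** The median is 0 if fewer than half trained and 1 if more than half did:

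| trained | median | pass under > | pass under ≥ |
|---|---|---|---|
| 20% | 0 | 20% | 100% |
| 40% | 0 | 40% | 100% |
| 60% | 1 | 0% | 60% |
| 80% | 1 | 0% | 80% |

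At the extremes, nobody trained (median 0) and everybody trained (median 1) give the same result: 0% pass under >, 100% under ≥.

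**5. Website use with many zeros.** Users are assumed to have 1 + Poisson(3) uses.

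| zeros | median | pass under > | pass under ≥ |
|---|---|---|---|
| 30% | 3 | 40% | 56% |
| 60% | 0 | 40% | 100% |
| 80% | 0 | 20% | 100% |

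**6. Median pooled over two equal arms.** For a normal item with an arm difference of d SD, the pooled median lies at d/2, so the share of intervention facilities above it is Φ(d/2):

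- d = 0.2: Φ(0.10) = 54%, against 46% of controls;
- d = 0.5: Φ(0.25) = 60%, against 40%;
- d = 1.0: Φ(0.50) = 69%, against 31%.

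Four such items give intervention means of 2.16, 2.39 and 2.77 out of 4, against 1.84, 1.61 and 1.23 in controls. Pooling therefore lets the index carry a between-arm contrast in the Adoption outcomes. That is still not a level of delivery.

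**The case against.** The strongest reply is that the index is only one summary, which the protocol itself calls crude, and that the plan has other evidence on delivery. Receipt and self-report are planned process measures, website use is tracked by facility and user type, the staff-training item asks what was done, and interviews follow at 1 year. Change in each secondary outcome is also to be examined separately. A relative score is a reasonable way to compare facilities.

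Much of this stands, and it rules out four stronger readings that a reader might infer:

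- *Delivery is never measured.* It is: receipt, self-report and website dose are planned, and website use feeds the index through the communication item.
- *Half of facilities fail every item by construction.* This holds for intent to refer and roughly for knowledge. It does not hold for the apparently yes/no training item or a usage count with many zeros, nor within each arm if the median is pooled. A fixed mean of 2 out of 4 needs all four items to be near-continuous, which the documents do not support.
- *The index selects the implementers and non-implementers for interview.* The plan says only that they come from consenting providers who completed the follow-up survey. It gives no classification rule and does not name the index as one.
- *A null primary result could not be interpreted.* The receipt, dose and interview data could be used to explore it; the limitation lies in the index.

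What the reply does not answer is that the index is the only quantitative measure in the Implementation row. The receipt measures are not listed there, their stated purpose is utility and satisfaction, and no criterion turns any of these data into a statement about delivery as intended.

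**Conclusion.** The point holds for the index as the Implementation measure. It reuses the Adoption outcomes, partly reflects response rather than delivery, and applies a sample-relative cut, so it can order facilities but cannot say how much was delivered. For near-continuous items the pass share is about 50% at any level. For tied items it depends on an unstated rule: with 60% of facilities training staff, the pass share is 0% or 60%; with 40%, it is 40% or 100%.

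The algebra for a continuous item and the yes/no arithmetic are exact. The knowledge, website and pooled-arm figures rest on assumed distributions, and the yes/no scale for training is inferred from how the question is described. A median fixed at baseline, which the text does not exclude, would let the index register change over time, but it would still set no standard for delivery. The consequence is confined to the implementation evaluation; neither the primary outcome nor the power statement uses the index.

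**What to change.** In the intervention arm, measure Implementation by scoring the planned delivery items yes/no against criteria fixed in advance:

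- intervention received;
- any staff use of the staff video;
- any patient use of the patient video;
- Medical Director reports passing the information to staff.

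Add webinar attendance and report download only if they will be logged. The documents say these materials will be available online but do not commit to recording either. State how receipt is established, which the documents also leave open, and give the denominator for each item, since the survey item exists only for consenting responders. Report the proportion of facilities meeting each item and the distribution of the total.

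List these items in Table 2's Implementation row. Keep knowledge and intent to refer under Adoption only, and acknowledge that video use and staff training inform both rows. The median-split index can be kept as a descriptive ranking, provided that the population for the median, the time point and the tie rule are stated.

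The cost is small: a redefinition that draws on data already planned. It loses comparability with the index as the protocol defines it, and some overlap with Adoption remains.

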Eligibility Criteria and Description of Potential Study Population – Facilities with at least n=11 patients (at least 4 AA patients) in their facility with a waitlisting disparity will be eligible for participation, since measured outcomes focus on disparity reduction and facilities with small proportions of AA or a small number of patients may be difficult to classify as a disparity facility. Of the facilities in the 18 ESRD Networks, n=1529 dialysis facilities had a racial disparity in waitlisting in 2014. Demographics of participating facilities with a racial disparity in waitlisting are: AA (42.3%) and 53.0% white; mean age 61.7 years; 65.5% unemployed, 11.4% Medicaid insurance; and 25.8% of patients waitlisted, and mean number of staff / facility 17.7. We expect ~1% of facilities will close in 1 year or there may be an improvement in racial disparities (from 2011) once we start the study, thus we expect a minimum of N=750 facilities will participate.

STUDY DESIGN AND METHODS

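### The primary analysis compares pre-to-post change between arms without naming the pre-year waitlisting gap as a covariate; adjusting for it could gain a little precision at almost no cost

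*Combined protocol and SAP*

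**What the plan says.** All references are to the combined protocol and SAP.

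- **Outcome** (Effectiveness Measure Outcomes, item 1): "We will calculate facility racial disparity in waitlisting one year prior and post-intervention as the difference between the proportion of AA vs. whites waitlisted". The pre-year value is therefore planned for every facility.
- **Analysis** (Statistical Analyses): the arms are compared, by intention to treat, on the "change in AA vs. white racial disparity reduction in waitlisting in the year post-intervention compared to the year prior to the intervention", "using generalized linear models⁴⁸ to account for potential correlation of facilities within Networks". No link function or covariate is given. Facility and patient characteristics enter only as modifiers in secondary analyses.
- **Randomisation** (Study Procedures): "we will randomize dialysis facilities that were not included in formative testing within each ESRD Network region".
- **Eligibility** (Eligibility Criteria): "Facilities with at least n=11 patients (at least 4 AA patients) in their facility with a waitlisting disparity" may enter, and "n=1529 dialysis facilities had a racial disparity in waitlisting in 2014".
- **Power** (Sample Size and Power): 80% with about 375 facilities per group, for a 10% difference in the AA/white waitlisting ratio at 1 year. The stated assumptions are a baseline ratio of 0.6 in both groups and an ICC of 0.06. No pre-post correlation is given and no credit is taken for baseline adjustment.

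**The concern.** A change score subtracts the pre-year gap in full, which fixes its coefficient at 1. A facility's gap rests on about 30 AA and 37 white patients, and eligibility allows as few as 4 AA patients, so part of the pre-year gap is sampling error. Subtracting it in full carries some of that error into the outcome. A model with the pre-year gap as a covariate estimates the coefficient from the data and discounts the noise.

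Reading the sentence as a linear two-period model with a free arm effect at baseline does not avoid the point. With both years observed for every facility, the arm-by-period term equals the difference in mean change. In one simulated data set of 750 facilities, the two analyses gave the same estimate (-0.000733).

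At stake is the width of the confidence interval for the primary contrast. The allowance for correlation within Networks is already planned and is not in question.

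**Working it through.** **1. The plan's own power figure.** Derive race-specific rates from 25.8% waitlisted, 42.3% AA, 53.0% white and a ratio of 0.6, placing other patients at the overall rate. This gives white 31.4% and AA 18.8%. With 70 patients per facility there are 29.6 AA and 37.1 white patients. Design effects by race are 1 + 28.6 × 0.06 = 2.72 and 1 + 36.1 × 0.06 = 3.17. For a ratio of 0.60 against 0.70 at 1 year, a Wald test on the log ratio has SE about 0.054. Then ln(0.70/0.60)/0.054 = 0.154/0.054 = 2.85, and power = Φ(2.85 − 1.96), about 81.4%. Reading 10% as relative (0.60 to 0.66) gives 41.4%. The stated 80% is thus recoverable as a post-year-only calculation on the ratio. It neither supports nor contradicts the change analysis.

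**2. General formula.** Let s₁ be the post-year SD, k = pre-year SD / post-year SD, and ρ the pre-post correlation.

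- Change score variance ∝ s₁²(1 + k² − 2ρk)
- Adjusted variance ∝ s₁²(1 − ρ²)
- Difference = s₁²(k − ρ)², which is never negative
- Proportional cut = (k − ρ)² / (1 + k² − 2ρk)

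Neither k nor ρ is in the documents, so they must be built from assumptions.

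**3. Sampling error of one facility's gap.** Placing other patients (4.7%) at the white rate, white = 0.258 / (0.423 × 0.6 + 0.577) = 0.311, AA = 0.6 × 0.311 = 0.186, and the mean gap is −0.124. The choice of rate for other patients hardly matters (compare step 1). Sampling variance = 0.186 × 0.814/29.6 + 0.311 × 0.689/37.1 = 0.0109, so SD = 0.104.

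**4. True between-facility SD of the gap.** An ICC of 0.06 gives facility-effect variances of 0.06 × 0.186 × 0.814 = 0.0091 (AA) and 0.06 × 0.311 × 0.689 = 0.0128 (white). With correlation c between the AA and white facility effects, the gap SD is √(0.0091 + 0.0128 − 2c√(0.0091 × 0.0128)):

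- c = 0: 0.148
- c = 0.5: 0.106
- c = 0.75: 0.076

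The documents do not give c. The range used is 0.03-0.148. SDs below about 0.076 need c above about 0.75.

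**5. Size of the gain.** Assume approximately normal gaps, a true gap stable over the two years, sampling errors correlated e = 0.5 or 0.8 between years, equal facility sizes, and selection on a pre-year gap below 0. Write S² for true plus sampling variance, r = (true variance + e × 0.0109)/S², a = 0.124/S and λ = φ(a)/Φ(a). Let v = 1 − aλ − λ² be the fraction of pre-year variance left after selection. The formula in step 2 becomes

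cut = v(1 − r) / [(1 + r) + v(1 − r)].

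Example, true SD 0.03 and e = 0.5: S = 0.109, r = 0.538, v = 0.672; cut = 0.672 × 0.462 / (1.538 + 0.310) = 16.8%.

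Example, true SD 0.148 and e = 0.8: S = 0.181, r = 0.934, v = 0.538; cut = 0.538 × 0.066 / (1.934 + 0.036) = 1.8%.

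| True gap SD | Sampling error as share of gap variance | Cut, e = 0.5 | Cut, e = 0.8 |
|---|---|---|---|
| 0.03 | 92% | 16.8% | 6.4% |
| 0.06 | 75% | 12.9% | 4.9% |
| 0.10 | 52% | 8.1% | 3.1% |
| 0.148 | 33% | 4.6% | 1.8% |

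Simulation of 2,000,000 facilities per cell agrees to about 0.1 percentage point.

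**6. In facilities.** Extra facilities = 750 × cut/(1 − cut). At 16.8% this is 750 × 0.168/0.832 = 151, and at 1.8% it is 750 × 0.018/0.982 = 14.

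**7. Finite-sample check.** This used 750 facilities of unequal size in 18 unequal Networks, randomised within Network, with 4000 null trials per cell and true SD 0.03-0.10. The adjusted model, with Network effects and robust standard errors, cut variance by 3-17% and had type I error of 4.0-5.0%.

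**The case against.** The strongest reply is that the plan contains no error here. The sentence in Statistical Analyses is short, a generalized linear model does not exclude a baseline term, and a two-period model with a common baseline mean across arms would already recover essentially the same precision. All of this stands. The point is that the term is not named, not that it is ruled out.

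The second reply is that the gain rests on figures the documents do not give, and that the one relevant figure they do give, the ICC of 0.06, points to the smaller end if AA and white facility effects are independent. This also stands, and is why the range runs down to about 2%.

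A reader might infer three stronger things, none of which the documents support:

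- *Selecting facilities with a disparity biases the comparison through regression to the mean.* Facilities are randomised within Network, so regression to the mean is expected equally in both arms and the contrast is unbiased.
- *Adjustment would lift the stated 80% power.* That figure is for a ratio at 1 year, whereas the outcome is defined as a difference. The plan claims no power for the change comparison.
- *The pre-year gap is mostly noise.* Sampling error is a substantial share of its variance, but about one third at SD 0.148 and about half at 0.10. It dominates only at smaller SDs.

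**Conclusion.** The point holds as a modest, low-cost gain in precision. The planned change comparison is valid. On a linear scale, adding the pre-year gap keeps the same arm contrast and cannot increase large-sample variance.

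The gain is about 2-17% of variance under the assumptions in the working. The upper figure needs AA and white facility effects to be strongly correlated and year-to-year errors to be only moderately so. The gain approaches 0 as k approaches ρ, for example when a facility's gap is very stable from year to year. The argument covers linear facility-level models; patient-level models and other links were not examined.

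**What to change.** State the primary model in the SAP: the post-year facility AA-white difference regressed on arm and the pre-year AA-white difference on the same scale, keeping the planned allowance for Network. The arm coefficient is the treatment effect. A two-period model with a common baseline mean across arms is an equivalent choice. If the outcome is finally analysed as a ratio, put the covariate on that scale.

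The cost is one degree of freedom out of about 730 (a variance increase of about 0.1%) and a sentence of wording. The pre-year value is already needed for the change score, so data collection, eligibility and sample size are unchanged. Naming the term in advance also removes an analyst's choice that could otherwise be made after the results are seen.
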